level of pain". The VAS scale will be used for both the SOC and intervention group to compare the pain level when starting the return line. The RN will collect a CBC before the start of the procedure which will be used in the programing of the TAP procedure. The RN will start recording the "inlet rate, return line pressures, and alarms" every 15 minutes until the procedure is completed.

Before patient disconnects, and after the completion of procedure sing the same therapeutic apheresis procedure access site, a blood sample will be drawn by the RN 2 lavender top tubes (4ml) for plasma hemoglobin test. The plasma hemoglobin test will be sent to the UTSW lab for analysis of hemoloysis and results will be sent back directly to the PI. Blood sample results will be collected by the PI or the study team in an excel spreadsheet (CRF) that will be saved on a secure drive on the UTSW campus.

Hemolysis is defined as the destruction of red blood cells which leads to the release of hemoglobin from the red blood cells into the blood plasma. Each patient will be tested for hemolysis by running plasma hemoglobin test after the procedure has finished. This will be collected in a two lavender tops (4ml) The cost for this test is covered by sponsor and because the patient has an indwelling access to venous blood there will no charge for drawing the sample.. There is no clinical suspicion that the use of the 20-gauge BD Nexiva Diffusics Catheter will increase this risk. Hemolysis will be scored dichotomously as present or absent for each encounter.

Pain is defined as any increase discomfort experienced by the patient associated with the apheresis procedure. The current standard of care is to ask the patient "are you having pain" and then ask them to rate the pain from 0 to 10. For this study, one additional question will be asked after the patient's vein has been accessed (IV catheter in place). The patient will self-report their pain using a 100 mm VAS scale. "*The VAS has been used by healthcare providers to measure the characteristics of disease severity in each patient individually*"(Klimek et al., 2017) Currently, all peripheral apheresis patients have some pain/discomfort while having a treatment, however; it is usually tolerated with minimal complaints.

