Measures of Quality of Apheresis will include inlet rate, and return pressures, procedure time. These measures are all readily available in the electronic medical record (EMR) and are all currently recorded as standard of care. The inlet rate is defined as the percent of patient inlet rate divided by the maximum allowable inlet rate. Because inlet rates are different for each type of TAP has a different maximum inlet rate, this will allow standardization across procedures. The max inlet rate for Photopheresis is 50ml/sec, the max inlet for plasma exchange is 100ml/sec inlet for red blood cell exchange is 55ml/sec. In addition, the inlet rate for each participant in the intervention arm will be compared to the average of their last 5 procedures. This measure will compare the efficiency of the SOC verses the intervention.

Inclusion Criteria

- Adult (≥ 18 years old)
- Speaks and reads English
- A patient of the Apheresis clinic at UT Southwestern University Hospital and Clinics
- Scheduled to receive TAP (therapeutic plasma exchange, red blood cell exchange and extracorporeal Photopheresis) as standard of care

Exclusion Criteria

- Prisoners
- Persons under the age of 18 years
- Patient who are actively involved in chemotherapy

Sources of Research Material

There are three sources of data for this study: electronic medical record (EMR) and paper-and-pen data collection from the patient's bedside (Data Collection form), and lab results provided by the UTSW laboratory via EMR. The EMR data that will be collected will include demographic information such as: age, sex, race, ethnicity, and admission diagnosis. The paper-and pen-data collection will include the patient self-reported pain level (VAS Scale), CBC collection, procedure data (minutes, inlet rate, return line pressures and alarms) total procedure time and post procedure sample. The paper-and-pen data collection form (Appendix 1) will record data only during patients TAP's encounter. Blood sample will be obtained from a SOC line. An additional 8 ml's for blood will be drawn from the patients for research purposes. Results from the bloodwork will be provided by the UTSW laboratory via the patient's EMR.

Recruitment Methods and Consenting Process

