For this study, patients will be recruited from the Apheresis Unit at UT Southwestern University Hospital and Clinics by a member of the research team. A member of the research team will screen the electronic medical record to determine a patient's eligibility. If a patient appears eligible for the study a member of the research team will discuss eligibility criteria with a member of the clinical team (nurse manger, nurse, physician, resident, fellow, social worker). The researcher will communicate with the clinical team to ensure eligibility: adult (≥18 years old), speaks and reads English, admitted to the Apheresis Unit at UT Southwestern University Hospital and Clinics at the time of consent. All patients in this study will be able to provide selfconsent (read and speak English).

When a patient is deemed eligible, a member of the research team will discuss consent and study procedures with that patient, in a place that is comfortable for the patient. After being approached by a member of the research team, patients will have up to next visit to consider participation in the study. The study team expects recruitment of 30 participants to last approximately 8 months. (Table 1)

Potential Benefits

There may or may not be a direct benefit to the participants in this study. Any additional blood test result that seems out of the norm will be shared with the nurse on duty or treating physician. We would also hope to share this with the greater research and clinical community in hopes of finding an alternative way for apheresis patients to have therapeutic apheresis procedures with less pain and no increase in adverse events.

Potential Risks

Risks associated with BD Cather:

Longer procedure time might occur if the inlet rate of the treatment is slower. The patient will be informed of this during the ICF process. With smaller catheters there's a risk of not obtaining the appropriate return rate for the patient. When the return rate is out of the SOC parameters the SOC apheresis equipment (Optia or Cellex) will alarm. If the alarm sounds 3 times the RN will decrease inlet rate by 5 ml/sec until the minimum threshold is reached (if needed), which is 50 ml/sec for plasma exchange and 35 ml/sec for RBC exchange and 20 ml/sec for photopheresis. If the alarm continues to when the minimum threshold is reached the catheter will

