be replaced with the SOC 18-gauge catheter. Obtaining blood samples may cause some discomfort, feeling lightheaded, fainting, bruising, clotting, and bleeding from the site of the needle stick and, in rare cases, infection. The risks are mitigated by drawing blood from a line that has already been established as part of SOC.

There is a low risk of breach in confidentiality. Subjects will be assigned individual study identification (SID) numbers and no personal identifiers will be included in the final summary.

Patients who are randomized to the 20-guage needle group and who fail the intervention will be given the 18-guage standard of care needle. At the patient's next visit, the patient will once again be randomized. If the patient is randomized into the 20-guage needle arm and fails the intervention a second time, the patient will be removed from the study.

Procedures to Maintain Confidentiality

Study participants will be given a study identification (SID) number. Only the approved study personnel and the principal investigator have access to the database linking the SID to the patient name. This database is kept on a protected drive on a password protected computer. Paper or hard copy participant records will be kept in a locked file cabinet in a locked office. If any identifying information is transmitted, it will be done so via secure e-mail and/or dedicated fax machines.

Statistical Analysis Plan

All data will be first collected on the DCF (Appendix I) and then entered into an electronic spreadsheet (e.g., MS Excel) which will be converted to SAS v 9.4 for analysis. All statistical analyses will be performed at UTSW in a location with secure data encryption capability. Initially, the data will be summarized first using standard measures of central tendency (mean, median, standard deviation, and interquartile range) for each variable. These will be examined to support the assumption of being approximately normally distributed. Baseline characteristics will be summarized using appropriate parametric and non-parametric measures.

The primary hypothesis is that the 20-gauge BD Nexiva Diffusics catheter provides the same efficacy of current practice with no increase in adverse events for patients undergoing therapeutic apheresis. This will be examined in 2 steps. First, ANOVA will be used to explore

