efficacy wherein efficacy is represented by 1) the plasma hemoglobin value, and 2) the amount of time (minutes) required to complete a TAP. Hence models will be constructed to compare the mean plasma hemoglobin values by group, and to compare the mean number of minutes to complete TAP by group. Second, ANOVA will be used to compare the mean number of adverse events subjects experience in each group (intervention vs control).

Finally, a planned secondary analysis is to examine if the percent of lumen occupied by the return catheter is associated with return pressures. The suggested standard is that a catheter occupies < 45% of the inner-lumen diameter (measured with ultrasound). Return pressures >400 mm Hg are considered problematic. Chi-square analysis will be used to explore the odds of experiencing a return pressure > 400 mm Hg when the return catheter occupies <45% of the inner-lumen diameter.

Item	Month 1-2	Month 3-6	Month 4-8	Month 9-11	Month 12-18
IRB approval	Х				
Consent/	Х	X			
Enrollment					
Randomization	Х	X	Х	Х	
Data collection	Х	Х	Х	Х	
Manuscript				Х	X
prep					
Study closeout					X

Project Timeline

Enrollment of first patient (month 1), enrollment of the last patient (month 12), completion of data analysis (month 14), and manuscript submission (month 18). The apheresis team see approximatley 3000 TAP treaments each year. Of these, approximately 1500 encounters will meet the primary inclusion criteria. We anticipate that it will take less than 1-year to complete the study.

Future directions

The intention of this pilot study is to test the 20-gauge BD Nexiva Diffusics Catheter performance and efficacy. The findings from this study will be used to provide additional preliminary data to BD to support a National Institutes of Health or Agency for Healthcare Research and Quality (AHRQ) application (pending 2017 AHRQ funding announcements). Stakeholder feedback will be provided through an optional de-identified report to all patients and families.

Presentation of data

It is anticipated that the results from this study will be presented to American Society for Apheresis at their annual convention. The results will also be summarized in a manuscript and submitted for peer-review publication to Journal of Clinical Apheresis.

Appendix 1

Patient Sticker

A Randomized Trial Examining Plasma Exchange using the BD Catheter In an Outpatient Apheresis Unit The "REPLACE" study

Date SID Procedure Type						

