Instructions:	Please complete the following form except for the VAS scale. Must be completed by patient to measure the characteristics of pain severity. Please circle option that apply.					
Collect CBC	Yes	Νο				
Catheter type	18 GA BD Autogard	20 GA BD Nexiva Diffusics				
Vein diameter w/tourniquet:	Vein diameter w/o turniquet:	Vein diameter Procedure Running:				
Asses pain after return placement						
Please rate your current pain by drawing a vertical line across the bar below						

vere		Extremely Severe		
		Procedure d	ata	
tart time:				
Inlet rate	Return line pressures	Alarms	Comments	
	tart time:	tart time: Inlet rate Return line	Procedure da tart time: Inlet rate Return Alarms line	

Total Procedure time:	Procedure en	Procedure end time:		Final Inlet Volume/Blood Processed:	
Collect post proceduer Plasma Hemoglobin	Yes		No		

References

- Golestaneh, L., & Mokrzycki, M. H. (2013). Vascular access in therapeutic apheresis: update 2013. *Journal of clinical apheresis, 28*(1), 64-72.
- Kalantari, K. (2012). The choice of vascular access for therapeutic apheresis. *Journal of clinical apheresis*, 27(3), 153-159.
- Keller, S. C., Williams, D., Rock, C., Deol, S., Trexler, P., & Cosgrove, S. E. (2018). A new frontier: Central line–associated bloodstream infection surveillance in home infusion therapy. *American journal of infection control*, 46(12), 1419-1421.
- Kramer, N. (2016). Monitoring Central Line-Associated Bloodstream Infections (CLABSI) in Home Infusion. *Infusion*, 22(4), 35-44.
- McDiarmid, S. (2015). Reduce the risk of infection by reducing the need for central lines: using ultrasound guidance to establish peripheral access in patients with sickle cell disease undergoing red cell exchange apheresis. *Journal of clinical apheresis*, *30*(2), 98-99.

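### Replacement of a failing 20G catheter by the 18G control catheter is foreseen but not counted as an outcome, so a conclusion of same efficacy could be drawn without reporting how often rescue was needed

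*Combined protocol and SAP*

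**What the plan says.** Under Potential Risks, the protocol says that smaller catheters carry "a risk of not obtaining the appropriate return rate for the patient". Repeated alarms lead the nurse to step the inlet rate down to a floor: 50 for plasma exchange, 35 for red cell exchange and 20 for photopheresis. The Study procedure section gives maxima of 100, 55 and 50. "If the alarm continues to when the minimum threshold is reached the catheter will" be exchanged for the 18G. The rule is then restated: "Patients who are randomized to the 20-guage needle group and who fail the intervention will be given the 18-guage standard of care needle". The patient is randomised afresh at the next visit, but one who "fails the intervention a second time, the patient will be removed from the study".

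The outcomes are listed in two places. Study procedure: "Measures of Quality of Apheresis will include inlet rate, and return pressures, procedure time". It adds that the inlet rate, as a percentage of the maximum, will be compared in the intervention arm with the average of the participant's last 5 procedures. Statistical Analysis Plan: efficacy is analysed by ANOVA, "wherein efficacy is represented by 1) the plasma hemoglobin value, and 2) the amount of time (minutes) required to complete a TAP", followed by the mean number of adverse events. The one secondary analysis relates return pressure above 400 mm Hg to how much of the lumen the catheter occupies, not to randomised arm.

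The plasma hemoglobin sample is taken at the end: "after the completion of procedure sing the same therapeutic apheresis procedure access site, a blood sample will be drawn". The form in Appendix 1 asks for the catheter type ("Please circle option that apply") and has columns for alarms and comments. As extracted, it shows no field for replacement.

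**The concern.** The hypothesis is that the 20G works as well as the 18G. The most direct evidence against it would be a 20G run that could not be finished on the 20G. The protocol says exactly what happens then, but no planned summary counts it. The encounter is completed on the comparator, and its minutes and plasma hemoglobin enter the comparison with the 18G's contribution included.

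Two uses of the pilot are affected. Its data are meant to refine and power a full trial, for which the failure share is a basic input. The stated motive is to offer peripheral treatment to more patients by dropping the 18G requirement, and a reader will want to know how often the 20G managed without the 18G.

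**Working it through.** **The plan's own figure.** 33 + 33 = 66 encounters agrees. No alpha, power, SD, margin or expected failure rate is given, so the 33 cannot be derived from the documents.

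**What each planned measure shows in a rescued run**

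| Measure | What it shows | What it misses |
|---|---|---|
| Minutes | Slow running before rescue, and the replacement itself if timed | Whether the run was slow or failed |
| Inlet rate against last 5 procedures | The step-down before rescue | Same ambiguity; the Statistical Analysis Plan has no between-arm test for it |
| Plasma hemoglobin | Hemolysis over the whole procedure | Which catheter contributed |
| Adverse events | Replacement, if the team chooses to count it | The term is not defined |

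**How much failure moves minutes.** From the documents: plasma exchange maximum 100 and floor 50, and 33 encounters per arm. Assumed, because the documents give none of these: 10 of 33 rescued; share of volume *f* processed before rescue; mean rate before rescue *r* as a fraction of maximum; 18G runs at maximum throughout; replacement time zero; CV of minutes 20% to 40%; independent encounters.

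- Extra time in a rescued run: e = f/r + (1 − f) − 1.
- Shift in the arm mean: 10e/33.
- Power: two-sided 5% t-test, 33 v 33, standardised difference = shift/CV. Power of 80% needs 0.70 SD, which is 14%, 21% or 28% of mean minutes at CV 20%, 30% or 40%.

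| f | r | e | Arm shift | Power at CV 20 / 30 / 40% |
|---|---|---|---|---|
| 0.10 | 0.75 | 0.033 | 1.0% | 5 / 5 / 5% |
| 0.10 | 0.50 | 0.10 | 3.0% | 9 / 7 / 6% |
| 0.50 | 0.75 | 0.167 | 5.1% | 17 / 10 / 8% |
| 0.50 | 0.50 | 0.50 | 15.2% | 86 / 52 / 33% |
| 0.75 | 0.50 | 0.75 | 22.7% | 99 / 86 / 62% |

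If each replacement cost 10% of a run (assumed), every shift rises by 10 × 0.10/33 = 3.0 points. The first row becomes 4.0% (power 8% at CV 30%) and the fourth 18.2% (68%). With 3 of 33 rescued and no replacement time, all five shifts lie between 0.3% and 6.8%.

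**Inlet rate.** Average rate over a rescued run = 1/(1 + e). For f = 0.50, r = 0.50 it is 1/1.5 = 67% of maximum, a clear signal, but a 20G run completed at an average of 67% would look the same. For f = 0.10 it is 1/1.10 = 91% (r = 0.50) or 1/1.033 = 97% (r = 0.75), although 90% of the volume ran through the 18G. Early rescue is hidden best on both measures.

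**What counting would give.** Exact 95% intervals for failures in 33 independent encounters: 0/33 has upper limit 1 − 0.025^(1/33) = 10.6%; 3/33 (9.1%) gives 1.9% to 24.3%; 10/33 (30.3%) gives 15.6% to 48.7%.

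Patients may contribute up to 10 encounters, and 30 participants are expected, so these are probably too narrow. Take effective n = 33/[1 + (M − 1)ρ], where M = Σm²/Σm over 20G encounters per patient and ρ is assumed to be 0.2 to 0.5. With 66 encounters spread evenly over 30 patients, M is about 1.63, effective n is 29.3 to 25.1 and the 0/33 limit is 11.8% to 13.7%. With 26 patients having 1 encounter and 4 having 10, M is about 3.68, effective n is 21.5 to 14.1 and the limit is 15.8% to 23.0%.

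**The case against.** The route to failure is measured. Inlet rate, return pressures and alarms are recorded every 15 minutes, and the inlet-rate comparison with the last 5 procedures is meant to show efficiency. Because a second failure removes the patient, the team must also know of each first failure. The form may let a replacement be recovered: both types could be circled, or a comment written. The extracted form is visibly broken, so the missing field deserves little weight. All this stands, and it narrows the gap to an unplanned summary of information the team must largely hold. It does not supply that summary.

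The size is also open to challenge. Every failure share is assumed, and a failure costing much time at a low CV would show in minutes: rescue at half volume at the floor has 86% power at CV 20%. Low power with 33 per arm affects any difference in minutes, and reading non-significance as sameness is a separate problem of having no margin. These points stand too. The argument rests on minutes being unable to tell slow from failed, not on any one power figure.

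Four stronger readings are tempting but unsupported:

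- A reader might infer that many 20G runs will fail. The documents give no rate.
- A reader might infer that rescued encounters would be dropped or moved to the control group. Nothing says so; analysis in the randomised group is the natural reading.
- A reader might infer that removal after a second failure distorts the failure share. At about 66/30 = 2.2 encounters per patient the effect is small: with a true share of 20%, the observed share is 20.0% at 2 encounters per patient and 18.6% at 3.
- A reader might infer that the completion share carries over directly to patients whose veins exclude an 18G. Every encounter can be allocated to, or rescued by, an 18G, so participants are by inference able to take one.

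**Conclusion.** The concern holds as a gap in the outcomes. The plan foresees replacement by the control catheter and has no measure that counts it, so same efficacy could be concluded without reporting how often the 20G needed rescue. How often that would happen cannot be known from the documents.

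Under the assumptions above, with 30% of 20G runs rescued, the power to notice through minutes runs from about 5% (early rescue) to above 80% (late rescue at the floor with a low or middling CV). These figures ignore the extra spread that a mix of rescued and unrescued runs adds to the 20G arm, which would lower power, and apart from the stated variation they ignore replacement time, which would raise it. The conclusion needs only the text and the fact that minutes, inlet rate and end-of-run plasma hemoglobin cannot isolate a failure.

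This is a cheap improvement to a pilot and should be made. It does not show that the planned comparisons are invalid.

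**What to change.** 1. In the Statistical Analysis Plan, add as a named efficacy outcome: procedure completed on the randomised 20G catheter without replacement. Report n/33 with a 95% interval that allows for repeat encounters per patient, or an exact interval labelled as assuming independence.
2. On Appendix 1, add: return catheter replaced yes/no, and time of replacement.
3. State with the result that the share applies to patients who could receive an 18G, and is only indirect evidence for patients whose veins rule it out.

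The cost is one form field, a few sentences in the plan and slightly more analysis. No extra patients, visits, samples or change in bedside handling are needed.

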To accomplish these goals, our outpatient clinic is open Monday thru Friday offering 4 different appointment times. All patients that are referred to our clinic for TAP, first receive a vein evaluation to see if the patient is a candidate for peripheral IV therapy. At our clinic, approximately 68% of our TAP's are performed peripherally. This eliminates the risk of a central line infection and any alteration in activities of daily living, such as bathing(Kramer, 2016), (Shang, Ma, Poghosyan, Dowding, & Stone, 2014),(Keller et al., 2018; McDiarmid, 2015).

Our hypothesis, is that the 20-gauge BD Nexiva Diffusics catheter provides the same efficacy as current practice with no increase in adverse events for patients undergoing therapeutic apheresis. The results from our study will be significant because if the 20 guage needle is equally effective for TAP, it can increase the number of patients that would be candidates for peripheral therapy. Therefore, decreasing the need for central venous access, which place the patient at an increased risk of infection. Our study is a comparison of 2 types of infusion catheters. The standard of care is an 18-gauge autogard catheter (control group) which will be compared to the 20-gauge BD Nexiva Diffusics (intervention).

- P patients who require therapeutic apheresis procedures (TAP)
- I use of 20G BD diffusics catheter during apheresis
- C use of 18 G standard of care IV catheter during apheresis
- O no difference in efficacy and no increase in safety events

Concise Summary of Project

This is a randomized pilot study of TAP using the current standard of care catheter (SOC) vs the BD Nexiva Diffusics Catheter. It is a single blinded, randomized study. Data will be used to refine and power a full randomized control trial. For this study, a sample of 33 encounters in each group (total of 66 encounters). Our specific aim is to test the hypothesis that the 20-gauge BD Nexiva Diffusics Catheter provides the same efficacy and lower pain level with no increase in adverse events for patients undergoing apheresis treatments.

Randomization Procedure

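### The primary hypothesis is one of sameness, but the planned ANOVAs take equal means as their null and the plan has no margin or confidence interval that could support it

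*Combined protocol and SAP*

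**What the plan says.** The Statistical Analysis Plan gives the hypothesis: "The primary hypothesis is that the 20-gauge BD Nexiva Diffusics catheter provides the same efficacy of current practice with no increase in adverse events". The outcome line of the summary list under Background and Significance puts it as "no difference in efficacy and no increase in safety events". The Concise Summary of Project makes it the aim of the study: "Our specific aim is to test the hypothesis that the 20-gauge BD Nexiva Diffusics Catheter provides the same efficacy". That sentence goes on to add lower pain, which is a superiority question and lies outside this point.

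The SAP examines the hypothesis in two steps. The efficacy step begins "First, ANOVA will be used to explore" efficacy, and the models are to "compare the mean plasma hemoglobin values by group, and to compare the mean number of minutes to complete TAP by group". For safety, "ANOVA will be used to compare the mean number of adverse events subjects experience in each group".

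No equivalence or non-inferiority margin, significance level, confidence interval or decision rule appears anywhere. The only numerical thresholds in the SAP, for lumen occupancy and return pressure, belong to a secondary analysis. The study is called a pilot: "Data will be used to refine and power a full randomized control trial".

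**The concern.** The claim to be supported is that the arms are alike, or that the new catheter is no worse. An ANOVA of two group means takes equality as its null, and failing to reject a null is not evidence for it. In a small study that failure is likely even when a real difference exists. The stated test therefore does not address the stated hypothesis, and the plan provides no other route to it.

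What is at stake is the wording of the conclusion. Background and Significance ties a practical consequence to it: "if the 20 guage needle is equally effective for TAP, it can increase the number of patients that would be candidates for peripheral therapy". Under Future directions, the findings are to serve as preliminary data for a grant application. The plan should say beforehand what evidence would justify the words equally effective.

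**Working it through.** **1. Hypothesis set against test.** For each outcome, let d be the 20G mean minus the 18G mean.

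| Outcome | What the hypothesis asserts | Null of the planned ANOVA |
|---|---|---|
| Plasma hemoglobin | d is close enough to 0 to call the same | d = 0 |
| Minutes to complete the procedure | d is close enough to 0 to call the same | d = 0 |
| Adverse-event count | d is not above 0 by an amount that matters | d = 0 |

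A significant ANOVA rejects exact equality but does not say whether the difference is larger than can be tolerated. A non-significant ANOVA is compatible with no difference and also with a sizeable one. Neither result supports the middle column. An interval for d set against a margin could, but the plan commits to neither.

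**2. The plan's own figure.** The Concise Summary of Project gives 33 encounters per group, 66 in total. This cannot be reproduced, because no alpha, power, effect size, SD or margin is stated.

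**3. Illustration of how little a non-significant result would show.** Taken from the plan: 33 encounters per arm. Assumed, because the documents are silent: two-sided 5%, independent encounters, differences in SD units.

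- Standard error of the difference: sqrt(2/33) = 0.246 SD.
- Degrees of freedom: 2 × 33 − 2 = 64, so t(0.975, 64) = 1.998.
- 95% interval half-width: 1.998 × 0.246 = 0.492 SD.
- Chance of a non-significant result when the true difference is 0.5 SD: the noncentrality is 0.5 × sqrt(33/2) = 2.03, the noncentral-t power is 51.6%, and 1 − 0.516 = 48.4%.
- Upper 97.5% exact bound on an event rate after zero events in 33 encounters: 1 − 0.025^(1/33) = 10.6%.

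**4. What the documents allow on clustering.** Patients are re-randomized at each encounter and may take part up to 10 times (Randomization Procedure). Recruitment Methods and Consenting Process expects 30 participants, so the planned average is 66/30 = 2.2 encounters per patient. The within-patient correlation and the spread of encounters across patients are not given. Because a patient can contribute to both arms, a model with a patient effect could be more precise than the figures in step 3. How much more cannot be worked out from the documents. Step 1 does not depend on this.

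**The case against.** The best defence is that this is a pilot. The efficacy ANOVA is described as exploratory, and a formal margin is not normally expected of 66 encounters. That stands as a limit on severity, and nothing here calls for a powered equivalence trial. It does not remove the mismatch, because the SAP still names a primary hypothesis and the stated aim is to test it.

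A second defence is that a two-group ANOVA yields a difference and its standard error, and that the SAP already plans means and SDs for each variable. This is also right. The ingredients of an interval would exist, and the SDs alone would go a long way towards powering a later trial. It would be too strong to say that the pilot could not inform one. What is missing is a commitment to report the difference with its interval and a statement of what it would have to show.

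A reader might infer that the sponsor intends to read p>0.05 as sameness. The documents do not support that: no p-value rule is stated. The fair criticism is that the plan offers no other basis for its conclusion and does not rule that reading out.

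A reader might also take 0.49 SD and 48% as properties of this trial. They are not. They rest on an assumed alpha and independent encounters, and for minutes the SD would mix three procedure types.

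**Conclusion.** The point holds as a mismatch between hypothesis and analysis. As written, no result of the planned ANOVAs can support the primary hypothesis, and the plan has no margin or interval with which to support it otherwise. This follows from the text alone and needs no assumed figures. The numerical illustration only shows that, at about this size, a non-significant result could easily coexist with a moderate difference or a non-trivial event rate. Whether differences of that size matter clinically is for the sponsor to say. Because the study is exploratory and no false decision rule is written down, it should be fixed but does not undermine the trial.

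**What to change.** Amend the Statistical Analysis Plan so that estimation is primary:

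1. Report the 20G minus 18G difference in plasma hemoglobin and in minutes, each with a 95% confidence interval, from a model with a patient effect and procedure type. An example is a linear mixed model with a patient random intercept, in the SAS 9.4 already planned.
2. Report the between-arm difference in mean adverse-event count per encounter, the unit that is randomized, with a 95% interval that accounts for patient.
3. State that a non-significant result will not be read as evidence of the same efficacy or of no rise in adverse events.
4. Allow an equivalence or non-inferiority conclusion only for an outcome whose margin the sponsor fixes and justifies before data are seen, and whose interval meets it. Otherwise report the pilot as estimation only.

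The cost is SAP wording, with no extra patients or visits. The downside is a weaker permitted conclusion, and any sameness claim will need a margin defended in advance. The adverse-event count also needs a definition of an event, which the documents do not give. The present ANOVA needs it too, so it is a separate matter.
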